13.5 Statistical Analysis Plan

With 24 evaluable patients treated we will estimate median time to treatment failure (radiographic or PSA progression, death or cessation of treatment due to clinical progression or toxicity). Our historical data suggest a 16 month median time to TTF [10]. Other studies varied in results and endpoints used, ranging from a median time to failure of 11 months [45], median distant progression free survival of 21 months [46], and median time to clinical progression of 18 months [23]. Even when permitting a lower PSA entry criteria ($PSA > 0.2$) the median time to progression was 21 months [14]. (Note: This observation has allowed us to amend this study to permit that lower PSA entry criteria to help with accrual). We seek to demonstrate a median TTF of at least 25 months, exceeding reports from all previous prior studies that examined only a two modality approach. With 24 evaluable patients, accrued over 16 months and followed for 18 months, we will have greater than 80% power to detect an improvement in TTF from 16 months to 32 months with a one-sided type I error of 10%. The critical value for a promising median TTF based on this design is 25 months, or an improvement of 9 months over our historical data. If patients experience treatment failure at ONLY an untreated asymptomatic low volume locoregional recurrence (allowed per amendment 6 based on PI discretion), TTF will be censored at that time for that patient.

Other secondary analysis will include progression-free survival, overall survival, complete response rate, duration of response, and duration of overall complete response, bone specific progression-free survival and duration of stable disease.

Exploratory analysis will include describing the rate of normalization of the total alkaline phosphatase level at the end of protocol therapy and evaluation of the role of genomic mutations and immune biomarker

studies on outcome and toxicity. These outcomes will be reported to provide further support, combined with the activity, and tolerability to help guide additional studies.

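### An observed median TTF of 25 months would reject 16 months only; it would not demonstrate a median of at least 25 or one longer than all earlier reports

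*Combined protocol and SAP*

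**What the plan says.** Section 13.5 takes its reference from the centre's own earlier trial, a median TTF of 16 months. It then lists other reports: 11 months to failure, 18 months to clinical progression, 21 months of distant progression-free survival, and 21 months to progression in a trial with a lower PSA entry level. The aim follows: "We seek to demonstrate a median TTF of at least 25 months, exceeding reports from all previous prior studies". The comparison is restricted to studies with two modalities ("exceeding reports from all previous prior studies that examined only a two modality approach").

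The design statement reads "With 24 evaluable patients, accrued over 16 months and followed for 18 months", and the trial is said to have "greater than 80% power to detect an improvement in TTF from 16 months to 32 months with a one-sided type I error of 10" per cent. The decision value is given as: "The critical value for a promising median TTF based on this design is 25 months", glossed as 9 months above the historical figure. The synopsis repeats the aim, the design and the decision value. Neither place names a confidence limit for the median, and neither gives an error rate against any median other than 16 months.

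**The concern.** The paragraph treats a cut-off for the estimate as if it were the parameter value that the trial would establish. A one-sided 10% test with a 16-month null can conclude that the median is longer than 16 months. It does not test whether the median is below 25, or whether it is no better than the largest earlier report. The 10% therefore does not attach to the conclusion named as the aim.

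What is at stake is the wording of the primary conclusion. With an observed median of 25 months, the plan as written leaves room to state that at least 25 months has been demonstrated and that all earlier two-modality results have been surpassed. The results are meant to help guide further studies, so the permitted claim should be fixed before analysis.

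**Working it through.** **Inputs.** From 13.5: n = 24, 16 months of accrual, 18 months of follow-up, null 16, alternative 32, one-sided 10%, cut-off 25, largest listed report 21. From 13.3: 66 months of accrual, and 68 months of treatment and follow-up for the last patient. Assumed here, not in the plan: uniform accrual, administrative censoring only, and exponential TTF unless another shape is named.

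**1. Expected events, stated timing.** With λ = ln 2 / M, d(M) = 24 × [1 − (e^(−18λ) − e^(−34λ)) / (16λ)]. This gives 16.06 events at M = 16, 13.71 at 21, 12.23 at 25 and 10.27 at 32.

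**2. The plan's own power.** The log of the estimated median has standard error of about 1/√d.
- 10% cut-off against 16: 16 × exp(1.2816/√16.06) = 22.0 months.
- Power at 32: Φ[(ln 2 − 1.2816/√16.06) × √10.27] = Φ(1.20) = 0.88. The stated power above 80% is reproduced for a 10% test against 16 months.
- The literal rule of an observed median of at least 25 is stricter. Its error at 16 is 1 − Φ[ln(25/16) × √16.06] = 1 − Φ(1.79) = 0.04; simulation gives 4.6% (exponential MLE) and 5.1% (Kaplan-Meier). Its simulated power at 32 is about 80% (MLE) and 76% (Kaplan-Meier).

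**3. True median exactly 25.** 1 − Φ[ln(25/25) × √12.23] = 0.50. The simulated Kaplan-Meier rule is met about 42–50% of the time over all the shapes and timings in the table below.

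**4. True median 21.** 1 − Φ[ln(25/21) × √13.71] = 1 − Φ(0.65) = 0.26. Simulated probability that the Kaplan-Meier median is at least 25 (100,000 trials per cell; repeat runs agree to about one percentage point):

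| Assumed TTF shape | 16 + 18 months | 66 + 18 | 66 + 68 |
|---|---|---|---|
| Exponential | 26% | 22% | 21% |
| No failures for 8 months, then exponential | 18% | 14% | 12% |
| Weibull, shape 1.5 | 18% | 15% | 13% |
| Weibull, shape 2 | 12% | 9% | 7% |

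With the exponential MLE in place of Kaplan-Meier, the first row is about 26–27%, 22% and 18%.

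**5. What an observed 25 supports.** The approximate one-sided 90% lower limit is 25 × exp(−1.2816/√d). With d = 12.23 it is 25/1.443 = 17.3 months; with 10.27 to 16.06 events it runs from 16.8 to 18.2. It clears 16 but not 21. To clear 21, the observed median must be about 21 × 1.443 = 30.3 months. Simulation puts that cut-off at 30.4 (MLE), with power of about 57% at a true median of 32.

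**The case against.** The strongest reply is that the plan already limits itself. The error rate is tied explicitly to 16 versus 32 months, 25 months is called promising, Section 13.1 speaks of preliminary efficacy, and no hypothesis about 21 months is stated. The phrase about earlier reports could mean only that 25 is numerically larger than the values listed. Any point-estimate threshold is met about half the time when the truth equals it. All of that is fair, and it is why the test against 16 months needs no change. It does not rescue the aim as worded, because the same paragraph says that the trial seeks to demonstrate both things.

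A reader might infer something stronger: that a regimen no better than the best two-modality treatment would pass at more than twice the stated 10%. The documents do not support that, for two reasons.
- Twenty-one months is not an established two-modality TTF median. One 21-month figure is distant progression-free survival after SBRT for treatment-naïve recurrence (reference 46). Section 2.4 describes the other, from the STOMP trial, as ADT-free survival and says that the trial used SBRT without concurrent systemic treatment. Under Table 12.1, TTF runs from the start of ADT and has its own PSA rule. The benchmark also moves with the endpoint: Section 2.4 gives a median 38-month deferral of ADT from the study that 13.5 cites for 18 months. The one listed report that the documents clearly describe as ADT plus radiation to metastases is the centre's own trial, which is already the null.
- A rate above twice 10% at 21 months needs roughly exponential failure from the start of ADT. With fewer failures during the initial ADT period the rate is about 7–18%.

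Nor can one infer that the rule is lax against its own null. At 16 months it is stricter than the stated 10%.

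**Conclusion.** The point holds as a mismatch between the stated aim and what the design can conclude. Meeting 25 months rejects a 16-month median. It does not show a median of at least 25, since the rule is met about 42–50% of the time when the truth is exactly 25, under every shape and timing tried. It does not show a median above 21 either; there the rate is about 18–26% under exponential TTF and about 7–18% under the alternative shapes. These percentages rest on assumed failure-time shapes, uniform accrual and administrative censoring only, and 21 serves only as the largest number in the plan's own list. The logical gap does not depend on them: no error rate or confidence bound is specified for any value above 16. The sample size and the test against 16 months are untouched. This should be corrected before analysis, because it determines what the primary result may be said to show.

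**What to change.** In Section 13.5 and in the synopsis:
- State that an observed median meeting the critical value rejects the 16-month reference only, and remove the sentence that begins "We seek to demonstrate a median TTF of at least 25 months, exceeding reports from all previous prior studies".
- Report the Kaplan-Meier median TTF with a one-sided 90% lower confidence limit. Name the interval method, and say whether the critical value or the limit governs the 16-month claim if they disagree.
- Allow a statement that the median exceeds any value above 16, such as 21 or 25, only if the lower limit is above that value. Note beside it that the cited reports use different endpoints and that the trial is not powered for that comparison.

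The cost is wording in two places and one confidence limit, with no extra patients, visits or data. The downside is that an observed median of 25 months will carry a weaker claim than the present text suggests.

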Despite its limitations hormone therapy and chemotherapy have been effective in eradicating subclinical deposits when used as an adjuvant to local therapy. But all too often the tumor recurs in a few locations, the likely consequence of the large number of tumor cells at these sites or limited drug availability at the site. These remaining oligometastases then may serve as a nidus for further dissemination. Metastatic prostate cancer is a heterogeneous disease and patients with ≤ 5 lesions have better survival than patients with > 5 metastatic lesions[9]. It is considered more likely that patients with limited number of metastases will benefit from local therapy to metastases.

We have previously reported results of a clinical trial in 29 patients with oligometastatic hormone sensitive prostate cancer treated at City of Hope with 36 weeks of androgen deprivation therapy (ADT) and external beam radiation therapy (EBRT) up to 45 Gy to all (≤ 5) metastases[10]. We concluded that treatment with radiation therapy to oligometastases was feasible. Ninety percent of patients treated with 36 weeks of ADT and EBRT to metastases achieved PSA nadir of <0.2 ng/mL that is known to be associated with good prognosis[11]. Four of 8 patients with metastases limited to pelvic lymph nodes remained in remission off ADT after a median follow up of 25.7 months. We postulated that patients with oligometastases represent distinct subset of hormone sensitive prostate cancer that may serve as a focus for clinical trials evaluating novel local and systemic therapies in combination with ADT. In our current trial we are now allowing patients with lower PSA (i.e. PSA >0.2) due to recent advances in imaging to detect oligometastatic disease at lower PSA levels.[13] Similar PSA levels were used as inclusion criteria in the recently published oligometastatic STOMP trial[14, 15].

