In the STOMP trial, prostate patients with oligometastatic recurrence of prostate cancer are eligible to receive SBRT[24]. The trial is limited to SBRT alone without concurrent systemic treatment. It is a randomized Phase 2 study to see if there is benefit of SBRT versus active surveillance of patients with

oligometastatic prostate cancer. The hypothesis is that patients treated with SBRT will have a longer ADT free survival and longer time to initiation of long term androgen deprivation use. The trial delineates radiation dose guidelines for lymph node and bone metastases. The dose is 10Gy x 3 fractions building from prior studies of this same groups utilizing this SBRT radiation dose with concomitant androgen deprivation therapy[24]. Toxicities from this SBRT regimen were mild and of 50 patients treated, only 10 patients had either Grade 1 or 2 toxicities[24]. The 50 patients had 70 metastatic lesions treated and local control of 100%; lesions included mostly bone and lymph nodes with only 2% visceral metastases; from 2005-2012 the dose was 50Gy in 10 fractions and from 2012-2014 the dose was 30Gy in 3 fractions. Our study is limiting to lymph node and bone metastases using similar radiation dose guidelines of both the STOMP trial and the NRG BR001 trial. The STOMP trial has now been published and demonstrated that SBRT to multiple metastatic sites (three or less) is safe and does delay metastatic progression and thus initiation of androgen deprivation therapy (ADT) (Ost et al 2018)[14]. The median ADT-free survival was 13 months for the observation/active surveillance group and 21 months for the metastasis-directed therapy group (either surgery, radiation or a combination)[14].

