13.3 Accrual and Expected Duration of Trial

The sample size is 24 evaluable patients (as of July 2023 we had 1 inevaluable patient, therefore we will need to accrue a total of 25 patients to get 24 evaluable patients). Accrual is expected to be completed in 66 months.

Participant duration is planned for 68 months which includes protocol therapy (~ 8 months) and follow-up (5 years).

The estimated total study duration will be 134 months (~ 11 years), with 66 months of accrual and approximately 68 months of protocol therapy and follow-up for the last patient.

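### The 25-month critical value in section 13.5 does not match the stated one-sided 10% error rate: as a rule it has about 5% error and 76–80% power, and the accrual period behind it is out of date

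*Combined protocol and SAP*

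**What the plan says.** Section 13.5, repeated under Statistical Considerations in the synopsis, sets out a single-arm comparison with a historical median TTF of 16 months. The alternative is 32 months and the type I error is one-sided 10%. On timing and power it says: "With 24 evaluable patients, accrued over 16 months and followed for 18 months", with power above 80%. It then gives the decision value: "The critical value for a promising median TTF based on this design is 25 months". The stated aim is to show a median of 25 months or more. No test, estimator or survival distribution is named, so 25 months is the only decision criterion in the plan.

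Section 13.3 gives a different timetable: "Accrual is expected to be completed in 66 months". Total study duration there is 134 months. The synopsis gives 48 months of accrual and a study of about 8 years. The power statement still uses 16 months in both places.

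Among its benchmarks, section 13.5 describes a 21-month figure from a randomised trial as a time to progression. Section 2.4 reports that trial as follows: "The median ADT-free survival was 13 months for the observation/active surveillance group and 21 months for the metastasis-directed therapy group".

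**The concern.** With a sample size, an event-time assumption, a one-sided error rate and a null median, the critical value follows once the test is chosen. If 25 months is not the 10% cut-off, then the error rate, the power and the threshold cannot all describe one rule. The practical risk is an ambiguous result: an observed median between the true 10% cut-off and 25 months would be significant under the stated test and below the stated threshold, and the plan does not say which governs. The number of events also depends on accrual and follow-up, so a cut-off derived for 16 months of accrual need not hold for 66.

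**Working it through.** **Inputs (section 13.5).** n = 24; accrual A = 16 months; follow-up F = 18 months; null median 16; alternative median 32; one-sided 10%, z = 1.2816. **Assumptions (not in the plan).** Exponential TTF, uniform accrual, 18 months of follow-up after the last entry, administrative censoring only.

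**Expected events.** With λ = ln 2 / median, P(event) = 1 − [exp(−λF) − exp(−λ(A+F))]/(λA).
- Median 16: 1 − (0.4585 − 0.2293)/0.6931 = 0.669, so d0 = 16.06.
- Median 32: 1 − (0.6771 − 0.4788)/0.3466 = 0.428, so d1 = 10.27.

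**Trying to reproduce 25 months at one-sided 10%.**
- Exponential maximum likelihood estimate (MLE), log scale: 16·exp(1.2816/√16.06) = 22.0 months. Power = Φ(ln(32/22.03)·√10.27) = Φ(1.196) = 88%.
- MLE, cube-root scale: 16/[1 − 1.2816/(3√16.06)]³ = 22.4 months, power 89%.
- Simulated MLE: 22.3 months, power 89%.
- Simulated Kaplan-Meier (KM) median: 22.1 months, power 86%. Other conventions for the median give 22.5 to 23.3.
- Test of survival at 16 months against 0.5, normal approximations: implied medians of 23.3 to 24.1 months, power 79–80%.
- Exact binomial at 16 months: 15 of 24 free of failure implies 23.6 months at 15.4% error; 16 of 24 implies 27.4 months at 7.6%. No step falls at 10%.

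Across the approximations that target 10% under the 16-month null, the cut-off runs from 21.1 (MLE, linear scale) to 24.1 months. Borrowing the variance from the 32-month alternative moves the log-scale MLE to 16·exp(1.2816/√10.27) = 23.9 months, and the cube-root version to 24.6, but such a cut-off no longer has 10% error under the null.

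**Trying one-sided 5% (z = 1.6449).** Cube-root MLE: 16/[1 − 1.6449/(3√16.06)]³ = 24.9 months with 80.0% power. Simulated MLE: 24.7 months, 81%. Simulated KM median: 25.1 months, 76%. So 25 months and roughly 80% power fit together at 5%.

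**What a 25-month rule delivers at 16 + 18 months.**
- MLE, cube-root check: error = Φ(−[1 − (16/25)^(1/3)]·3√16.06) = Φ(−1.66) = 4.8%; power = Φ([(32/25)^(1/3) − 1]·3√10.27) = Φ(0.825) = 80%. Simulation gives 4.6% and 79.9%.
- KM median, simulated: 5.2% and 76.4%; other conventions 5.7–6.7% and 77.6–78.4%. These count a median not reached as a success. Under a true median of 32 months, only 25.8% of trials have an observed median that is reached and is at least 25.
- Test of survival at 16 months: a 25-month median implies S(16) = 0.5^(16/25) = 0.642, and (0.642 − 0.5)/√(0.25/24) = 1.39, an error of about 8%.

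**Current timing.** With A = 66 and F = 18, the event formula gives 20.4 events under the null and 15.3 under the alternative.

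| Timing (months) | 25-month rule: error, power (MLE) | 25-month rule: error, power (KM) |
|---|---|---|
| 16 + 18 | 4.6%, 80% | 5.2%, 76% |
| 48 + 18 | 2.5%, 82% | 3.8%, 75% |
| 66 + 18 | 2.1%, 83% | 3.7%, 74–75% |

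At 66 + 18 the 10% cut-off is 21.1 months (MLE) or 21.7 (KM).

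**What an observed 25 months shows.** One-sided 90% lower limit = 25·exp(−1.2816/√d). With about 15 events this is 18.0 months; with 12 events 17.3, with 17 events 18.3. That excludes 16 months, but does not establish a median of 25 or more.

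**The case against.** The strongest reply is that the mismatch is harmless. The error of a 25-month rule is below the stated 10% on every method tried, so a false claim of promise becomes less likely. The power shortfall is at most about four points at the stated timing and close to nil with the exponential MLE. This is a small single-arm phase 2 trial, and section 13.5 gives a reason to aim at 25 months: it lies above all the earlier results it cites. These points stand and limit the severity. They do not make the stated figures agree.

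Several stronger readings are tempting and are not supported.
- **Power of only 75%, so an active regimen is missed one time in four.** That is the low end; at the stated timing 76–80% is fair, because no estimator is named.
- **A cut-off of exactly 22 months.** For the same reason, tests of survival at 16 months put it nearer 24.
- **A median of 22 to 25 months would be reported as negative.** The plan contains no rule for a negative result; it only calls 25 months promising.
- **Longer accrual weakens the design.** It adds events. The fault is an outdated and inconsistent assumption.
- **The 16-month null is biased because the 29-patient predecessor trial included node-only patients, who lack the bone lesion required here.** Section 2.1 says: "Four of 8 patients with metastases limited to pelvic lymph nodes remained in remission off ADT after a median follow up of 25.7 months". If those patients did better, removing them would lower the null and make 16 months conservative. The documents give no median for patients with bone lesions, so the direction is unknown.

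**Conclusion.** The concern holds as an inconsistency among stated figures. Under exponential TTF and the stated timing, the one-sided 10% cut-off is about 22 months for the KM median or MLE and up to about 24 for tests of survival at 16 months. The 25-month rule has about 5% error (about 8% for tests of survival at 16 months) and 76–80% power. The documents cannot show whether the error rate or the cut-off is the slip. At 66 + 18 months the same rule has about 2–4% error and about 75% (KM) to 83% (MLE) power, so the gap from the stated 10% widens. The discrepancy is conservative and cheap to correct. It should be fixed before the primary analysis, but it does not threaten the trial. The label on the 21-month benchmark is a minor wording correction, since 21 months is not the null.

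**What to change.** 1. Name the primary test and estimator, and say how a median that is not reached is treated.
2. Then choose one of two routes. (a) Use a one-sided 10% test against an exponential with median 16, for example the one-sample log-rank test, which adapts to actual follow-up. Its simulated error is about 8–9%, with power about 88% at 16 + 18 months and 94% at 66 + 18. Report the KM median with a one-sided 90% lower limit. (b) Keep 25 months and restate its properties: about 5% error and 76–80% power at the stated timing, recomputed for current accrual.
3. State when the primary analysis takes place, for example 18 months after the last patient enters, and align accrual and duration across the synopsis, section 13.3 and section 13.5.
4. Reword the aim as showing that median TTF exceeds 16 months.
5. Label the 21-month benchmark in section 13.5 as ADT-free survival, as in section 2.4.

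The cost is a short recalculation and changes of wording; no further patients are needed. The downside is that the stated figures and the claim become slightly more modest.

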14.0 DATA HANDLING, DATA MANAGEMENT, RECORD KEEPING

14.1 Source Documents

Source documents are original documents, data, and records (e.g., medical records, pharmacy dispensing records, recorded data from automated instruments, laboratory data) that are relevant to the clinical trial. The investigator or their designee will prepare and maintain adequate and accurate source documents. These documents are designed to record all observations and other pertinent data for each patient enrolled in this clinical trial. Source documents must be adequate to reconstruct all data transcribed onto the case report forms.

